3.4 Medication regimen

Queue 1:

- Phosphorotapirata Palonosetron for Injection: Administered via intravenous infusion for 1 hour (+10 minutes), once before each chemotherapy cycle.
- Dexamethasone acetate: Oral administration of 12 mg on the first day of each chemotherapy cycle prior to chemotherapy, followed by 3.75 mg twice daily (bid) on days 2-4.

Queue 2:

- Fosapirita and Nifedipine for Injection: 150 mg, administered via intravenous infusion over 20-30 minutes, once before each chemotherapy cycle.
- Palonosetron hydrochloride: 0.25 mg, administered via intravenous push infusion for at least 30 seconds, once before each cycle of chemotherapy.
- Dexamethasone acetate: Oral administration of 6 mg on the first day of each chemotherapy cycle prior to chemotherapy, 3.75 mg once on the second day, and 3.75 mg twice daily (bid) on days 3-4.

3.5 Study Endpoints

[figure not shown]
Primary efficacy endpoint

The proportion of subjects achieving complete remission (CR: no vomiting and no rescue therapy) with an ultra-long delay period (120 h-168 h) after chemotherapy initiation in each immunotherapy plus chemotherapy cycle.

Secondary efficacy endpoint

- (1) CR rates during the acute phase (0-24 h), delayed phase (24 h-120 h), overall phase (0-120 h), and 0-168 h periods of each immunotherapy + chemotherapy cycle;
- (2) Comparison of the time to first vomiting using Kaplan-Meier curves;
- (3) Assess the impact of chemotherapy-induced nausea and vomiting on quality of life using the Functional Life Index-Vomiting (FLIE);
- (4) Incidence of adverse events and serious adverse reactions throughout the study period, such as safety concerns including prolonged Q-T interval and constipation.

3.6 Research Flowchart

3.7 Statistical Analysis

Count data were summarized using frequency and percentage. Measurement data were summarized using mean, standard deviation, median, maximum value, and minimum value. Statistical analysis was performed using SAS 9.4 software.

Population analysis

Full Analysis Set (FAS): Includes all enrolled subjects who received the investigational drug, with primary efficacy analysis based on FAS.

Safety Analysis Set (SS): Includes all enrolled subjects who received at least one dose of the study drug.

Efficacy Analysis

If a participant's assessment of vomiting episodes is missing on any day during the overall period, resulting in an inability to determine whether the participant has achieved complete remission, the participant is recorded as having incomplete remission.

Sensitivity analysis for primary estimation targets: The sensitivity analysis methodology is identical to that of the primary estimation method, with only differences in the missing value imputation rules. If a participant's assessment of vomiting episodes is missing on any day during the study period, complete remission is determined based on the available data from that participant.

If the subject's assessment of vomiting episodes is missing on any day within the extended delay period, resulting in an inability to determine whether the subject has achieved complete remission, the subject is recorded as having incomplete remission.

safety analysis

AEs will be coded using the MedDRA dictionary. The frequency and incidence of

treatment-emergent adverse events (TEAEs) will be summarized by grouping according to System Organ Classification (SOC), preferred terms, and severity. Outcomes such as vital signs, electrocardiogram (ECG), and other clinical laboratory tests will be summarized by relative changes from baseline. Additionally, abnormal clinical laboratory test results will be described in a separate table.

4 Sample Size Calculation

This study adopted a randomized, parallel, cohort design. Based on data from previous Phase III studies, the super-delayed complete response (CR) rate for HR20013+ dexamethasone in the first cycle for preventing nausea and vomiting induced by highly emetogenic chemotherapy was 90.3%, while the CR rate for fosapitant + dexamethasone + palonosetron was 86.5%. With a planned enrollment of 57 subjects per group, the 95% confidence interval (CI) width for the CR rates in both groups could be maintained within 0.2. Considering a 5% dropout rate, a total of 60 subjects were enrolled per group, resulting in a total of 120 subjects.

5 Data Management and Confidentiality

The sponsor was responsible for the clinical trial data management in this study, utilizing an Electronic Data Collection (EDC) system for data collection and management. All records pertaining to subject identity were kept confidential and not disclosed beyond the scope permitted by applicable laws and/or regulations.

5.1 Data Collection

The electronic Case Report Form (eCRF) shall be completed by investigators or data entry personnel through the Electronic Data Capture (EDC) system. eCRFs must be filled out promptly, with ensured traceability of data from original documents or records. When modifying data in the EDC system, the reasons for modifications must be documented according to system prompts. Modification history and rationale shall be recorded in the EDC system's audit trail. Investigators or their authorized personnel are required to verify the authenticity, completeness, and timeliness of eCRF data and affix electronic signatures within the EDC system.

Data administrators established electronic case report forms (eCRFs) and logical verification procedures in the Electronic Data Capture (EDC) system in accordance with the study protocol, completing user acceptance testing and system deployment prior to the first participant enrollment. All EDC users must complete relevant training and archive training records to obtain access permissions for the study's eCRFs. When implementing electronic signatures on eCRFs, users must confirm and agree to the electronic signature usage statement. Accounts are restricted to individual users only, with passwords requiring secure storage and regular renewal. Permissions must be promptly revoked when there are personnel changes within the research team.

5.2 Data Management

The logical verification program of the EDC system conducts integrity and logical checks on

entered data, raising questions about potentially problematic entries. Researchers or data entry personnel may correct data or provide explanations and confirmations by responding to these queries. Researchers must promptly address questions from both the system and data reviewers, and may raise follow-up questions multiple times as needed until all data issues are resolved.

Forty percent of participants will undergo an interim analysis upon completing the study. Prior to database locking, the research team must complete data cleaning, compile all protocol deviation events occurring during the trial, and convene a data review meeting to determine the analytical population. All decisions made during the data review meeting must be documented in written records. Following approval of the data review meeting, the research team will confirm the locking of the study database in the Electronic Data Capture (EDC) system. Once locked, the data cannot be modified.

Upon completion of the study, the storage and management of research materials must comply with Good Clinical Practice (GCP) requirements. Investigators must notify the sponsor in advance when destroying any study-related documents or records. After the investigational drug is approved for marketing, or even if the clinical study is terminated prematurely, the sponsor shall retain clinical trial data for at least 5 years.

6 Previous and concomitant therapies

6.1 Previous Treatment

Information on medication and non-pharmacological treatments administered by subjects during the 30 days prior to randomization must be recorded in the Electronic Case Report Form (eCRF). Prohibited treatments and prohibited medications prior to randomization were consistent with the exclusion criteria.

6.2 Remedial Treatment

Remedial treatment is defined as any prescription medication prescribed by the investigator to alleviate nausea/vomiting. This definition must be explained to the subject. During the study period, investigators evaluate the reported severity of nausea/vomiting and observed clinical manifestations. Remedial treatment for nausea/vomiting may be administered only when necessary based on investigator judgment, and must not be used if the subject does not exhibit such symptoms. When administering remedial treatment, 5-HT₃ receptor antagonists (excluding palonosetron) are recommended as the first-line option.

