Criteria for discontinuation of study treatment	
Participants have the right to terminate study treatment at any time for any reason. Reasons for terminating study treatment by participants include but are not limited to:
 
(1) The subject requested to terminate continued treatment;
 
(2) Occurrence of pregnancy events in subjects during the study process;
 
(3) Situations where the investigator deems it necessary for the subject to discontinue treatment:
 
 a. Occurrence of any adverse event, abnormal laboratory findings, or other medical conditions that may result in continued medication use no longer being beneficial for the subject, or pose significant risks to health or safety; b. Discovery of more severe protocol violations renders the participant unsuitable for continued trial participation; c. Other circumstances in which continuing the trial would significantly affect the health or safety of the subjects.

Exit study criteria	
(1) The subject voluntarily withdrew and refused further follow-up;
 
(2) Loss to follow-up;
 
(3) Death;
 
(4) Early termination of the study by the sponsor.

Effectiveness Evaluation	
Primary endpoint
 
 The proportion of subjects achieving complete remission (CR: no vomiting and no rescue therapy) during the hyperdelayed period (120 h-168 h) after chemotherapy initiation in each immunotherapy plus chemotherapy cycle; 
secondary endpoint
 
 The CR rates during the acute phase (0-24 h), delayed phase (24 h-120 h), overall phase (0-120 h), and 0-168 h periods of each immunotherapy plus chemotherapy cycle; The time to first vomiting was also compared using Kaplan-Meier curves. The Functional Life Index-Vomiting (FLIE) was used to assess the impact of chemotherapy-induced nausea and vomiting (CINV) on quality of life.
safety evaluation	
The incidence rates of adverse events and serious adverse reactions during the entire study period, such as safety concerns including prolonged Q-T interval and constipation.

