1.2.3.4 Metabolite Study of HRS5580 in Animals

HRS5580 undergoes extensive metabolism in rats, with 27 metabolites detected. The primary metabolic pathways include hydrolysis to form rolapipitan (M1), followed by further metabolic processes such as mono-oxidation (M2), dehydrogenation (M3), mono-oxidation coupled dehydrogenation (M4), and dual oxidation coupled dehydrogenation (M5), with the majority excreted via feces. In both rat and rhesus monkey plasma, the predominant metabolite is the hydrolyzed rolapipitan. Only trace amounts of the parent drug HRS5580 were detected in pooled blood samples collected within 2 hours after intravenous administration, while no HRS5580 was detected in urine or fecal samples.

2 Research Objectives

To evaluate the efficacy and safety of fosfoprolaplatin palonosetron for injection in preventing nausea and vomiting induced by multiple cycles of immunotherapy plus chemotherapy

in patients with esophageal cancer and lung cancer.

3 Study Design and Methods

This study is a randomized, parallel, cohort study designed to enroll 120 subjects, with 60 subjects per cohort. An interim analysis will be conducted when 40% of the subjects complete the study.

The trial consists of a screening phase, treatment phase, and safety follow-up phase. Pharmacotherapy is administered according to the trial protocol, followed by corresponding follow-up and examinations as specified in the trial schedule. During the study period, if the investigator determines that the subject indeed requires rescue antiemetic medication, rescue treatment may be provided based on clinical circumstances. The specific type, administration method, dosage, and frequency of the medication are determined by the investigator.

Study period: June 2025-September 2026

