3.2 Exclusion Criteria

Participants who meet any of the following criteria during screening and randomization are ineligible to participate in this study:

(1) Received or planned to receive abdominal (including diaphragmatic plane and below) or pelvic radiotherapy within the previous 7 days prior to randomization, or during days 1 to 8 of treatment;

(2) Schedule administration of highly emetogenic chemotherapy agents within days 2 to 8 after platinum infusion;

(3) Planned to receive chemotherapy regimens including conventional paclitaxel (using castor oil as solvent);

(4) Randomly administer drugs with potential antiemetic effects within the preceding 2 days: first-generation 5-HT₃ receptor antagonists (e.g., ondansetron), phenothiazines (e.g., prochlorazine), butyrophenones (e.g., haloperidol), benzamide derivatives (e.g., metoclopramide), domperidone, cannabinoids, traditional Chinese medicines with potential antiemetic effects, scopolamine, and cecirizine.

(5) Had started treatment with benzodiazepines or opioid preparations within the preceding 2 days (excluding triazolam, temazepam, or midazolam taken alone daily);

(6) Subjects who began morphine use within the preceding 7 days (excluding those on stable dosage regimens);

(7) Received systemic corticosteroid therapy (including but not limited to dexamethasone, hydrocortisone, methylprednisolone, or prednisolone) or sedative antihistamines (such as diphenhydramine) within the preceding 7 days (Note: Single-dose steroid administration for contrast agent allergy prophylaxis and topical or inhaled administration are permitted), except for cases requiring hormone pretreatment on the day before chemotherapy.

(8) Palonosetron use within the preceding 14 days;

(9) Use of NK-1 receptor antagonists within the preceding 28 days;

(10) Use of specific CYP3A4 substrates (terfenadine, cisapride, astemizole) or CYP3A4 inhibitors (e.g., ritonavir, clarithromycin, ketoconazole or itraconazole, diltiazem) within 7 days prior to randomization, or use of CYP3A4 strong inducers (e.g., phenobarbital, rifampin, phenytoin, carbamazepine) or specific CYP2D6 substrates (thiuridazine, pimozide) within 28 days prior to randomization;

- (11) Vomiting and/or retching, nausea occurring within the preceding 24 hours;
- (12) Subjects with symptomatic brain metastases;

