6.3 Contraindicated Medications in the Study

1. The use of rescue medications for non-rescue purposes is prohibited during chemotherapy;
2. During chemotherapy cycles, the use of medications containing rolapitan, palonosetron, or dexamethasone is prohibited except for visits specified in the treatment regimen.
3. The following medications are prohibited during the study period:
 - (1) Specific CYP3A4 substrates: terfenadine, cisapride, astemizole;
 - (2) Strong CYP3A4 inducers: phenobarbital, rifampin, phenytoin, and carbamazepine;

- (3) CYP3A4 inhibitors: ritonavir, clarithromycin, ketoconazole, itraconazole, diltiazem, etc.;
- (4) Specific CYP2D6 substrates: thioridazine, pimozide.

7 Informed Consent

The rights, safety, and physical/mental well-being of participants are paramount considerations, taking precedence over scientific and societal benefits. After explaining the fundamental aspects of the study and confirming participants' understanding of its objectives, investigators must require each participant to sign their name and date on the Informed Consent Form (ICF). Participants should carefully review and consider their informed consent statement before signing, and obtain a signed ICF. Prior to initiating any clinical study-related procedures, a signed ICF must be obtained from participants, including informed consent for any screening processes conducted to determine eligibility for study participation. Participants may not proceed with the study without obtaining informed consent.

For subjects who are unable to sign the informed consent form independently for any reason, the legal guardian must sign on their behalf. The ICF signed by the subject and the investigator with their names and dates must be properly retained by the investigator and documented in the relevant original research records.

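### Rescue is defined only as investigator-prescribed prescription medication, so a non-vomiting patient who takes an antiemetic from another source is scored a complete response

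*Protocol*

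**What the plan says.** The synopsis sets the primary endpoint as the proportion with "complete remission (CR: no vomiting and no rescue therapy) during the hyperdelayed period (120 h-168 h") in each cycle. Section 3.5 repeats it, and the secondary CR endpoints for the other windows use the same term. Neither place gives its own definition of rescue.

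The only definition is in section 6.2: "Remedial treatment is defined as any prescription medication prescribed by the investigator to alleviate nausea/vomiting". The next sentence reads "This definition must be explained to the subject".

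Four other places bear on the point:

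- **Section 3 (Study Design and Methods)** treats rescue as the investigator's decision: "The specific type, administration method, dosage, and frequency of the medication are determined by the investigator".
- **Section 6.3, item 1** states: "The use of rescue medications for non-rescue purposes is prohibited during chemotherapy". Its other items cover products containing the study antiemetics or dexamethasone, and certain CYP3A4 and CYP2D6 drugs.
- **Section 3.2, exclusion 4** lists products regarded as potentially antiemetic, among them domperidone and "traditional Chinese medicines with potential antiemetic effects". It applies to the 2 days before randomization.
- **Section 6.1** requires that treatments "during the 30 days prior to randomization must be recorded in the Electronic Case Report Form (eCRF"). It covers prior treatment only.

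**The concern.** The section 6.2 definition has two conditions: the product must be a prescription medication, and the investigator must have prescribed it. An antiemetic that fails either condition is not rescue, so taking it does not break CR. The patient has nevertheless had symptoms treated, and CR is meant to exclude that.

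The primary window is days 6-7 after chemotherapy. It is reasonable to infer, though the protocol does not say so, that many patients are then away from the centre and could obtain an antiemetic elsewhere. Because the narrow definition is explained to subjects, what they report as rescue may follow it too.

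At stake is whether the primary endpoint measures what its name implies. The sample size is built on estimating each arm's CR rate to a stated precision, so a one-directional error in those rates matters even when both arms share it.

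**Working it through.** **1. Does any other text widen the definition?**

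| Place | What it covers | Closes the gap? |
|---|---|---|
| Synopsis and 3.5 | CR needs no vomiting and no rescue | No; rescue is not redefined |
| Section 3 | Need for and choice of rescue rest with the investigator | No; same framing as 6.2 |
| 6.3 item 1 | Bars rescue drugs for purposes other than rescue | No; use for symptoms is not addressed |
| 3.2 exclusion 4 | Antiemetic products in the 2 days before randomization | No; eligibility only |
| 6.1 | Recording of treatments before randomization | No; nothing on the CR windows |
| 3.7 | Scoring when vomiting assessments are missing | No; silent on antiemetic use |
| 5.2 | Deviations compiled and reviewed before lock | No; no link to CR scoring |

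So the literal rule stands. No vomiting, no investigator-prescribed rescue and an antiemetic from another source is scored as CR.

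**2. The plan's own figures (section 4).** Inputs: n = 57 per group, assumed CR 90.3% and 86.5%, target 95% CI width within 0.2, dropout 5%.

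- Wald width = 2 × 1.96 × √(p(1−p)/n). For p = 0.903 it is 0.154; for p = 0.865 it is 0.177.
- Clopper-Pearson widths are 0.170 and 0.193.
- 57 / 0.95 = 60.

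The stated 57 and 60 reproduce, and this point does not change them.

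**3. Size of the error within an arm.** Let q be the share of an arm with no vomiting and no investigator-prescribed rescue who took another antiemetic for symptoms in the window. Then

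scored CR = CR under the wider definition + q.

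Since q cannot be negative, the error can only be upward. The protocol gives no value for q, so these are assumptions:

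| Assumed q | Patients of 57 | Scored 90.3% becomes | Scored 86.5% becomes |
|---|---|---|---|
| 1% | 0.6 | 89.3% | 85.5% |
| 2% | 1.1 | 88.3% | 84.5% |
| 5% | 2.9 | 85.3% | 81.5% |
| 10% | 5.7 | 80.3% | 76.5% |

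For scale, the Wald half-width for the comparator is 0.177 / 2 = 0.089, or 8.9 points. A shift of 2 to 5 points lies inside that interval, but it is systematic and more patients would not remove it.

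**4. Difference between arms.** With shares q₁ (test) and q₂ (comparator),

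difference under the wider definition = scored difference − (q₁ − q₂).

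Take the planning rates as the scored values: 90.3 − 86.5 = 3.8 points.

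- q₁ = q₂ = 5%: 3.8 points, unchanged.
- q₁ = 5%, q₂ = 0%: 3.8 − 5 = −1.2 points.
- q₁ = 0%, q₂ = 5%: 3.8 + 5 = +8.8 points.

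Bias in the comparison therefore needs unequal shares, and it could go either way.

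**The case against.** The best defence is that the protocol routes antiemetic treatment through the investigator. Sections 3 and 6.2 make rescue a matter of investigator judgement, so self-medication can be read as a deviation, and section 5.2 has deviations compiled and reviewed before lock. This stands in part. A reader might infer that such use is neither barred nor seen, and the documents do not support that. But nothing says that a deviation of this kind turns a CR into a failure, so the scoring gap remains.

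On recording, a reader might infer from section 6.1 that antiemetic use on study is not captured. That cannot be said: the section 3.6 flowchart is not available in the text reviewed, and on-study medication may be recorded under it.

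Exclusion 4 is modest support. It is a pre-randomization washout, not a statement of what counts as rescue, and the protocol does not say which listed products can be had without a prescription. A listed prescription drug that the investigator prescribes for symptoms is rescue under section 6.2.

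The size rests wholly on an assumed share. No hypothesis or margin is built on the 3.8-point planning gap, so that gap only illustrates scale.

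A reader might also infer bias between arms, because no blinding is described and the infusion schedules differ visibly (section 3.4). The protocol gives no evidence that knowledge of the arm changes self-medication, and no direction. This is a possibility, not a finding.

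Finally, the English reads as a translation, and the narrow wording may come from that. It is still the operative text, and it is explained to subjects.

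**Conclusion.** The point holds as a flaw in a stated endpoint rule. It is not a detail left to a statistical analysis plan, because the protocol fixes the definition and has it taught to subjects. Its scope is limited to patients with no vomiting and no investigator-prescribed rescue in the window; anyone with either already fails CR. It would go too far to say that every patient who takes an outside antiemetic is scored as a CR.

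For the affected patients the direction within an arm is certain and the amount is not known. An assumed 2% to 5% gives an overstatement of 2 to 5 points, about 1 to 3 of 57 patients per arm. It affects every CR window and cycle, with 120-168 h the one that matters most. The comparison between arms is affected only under unequal use, which the documents neither show nor rule out. The point should be corrected, with medium confidence in its practical importance.

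**What to change.** For endpoint scoring only:

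1. In section 3.5 and the synopsis, define the event that fails CR as any antiemetic taken to relieve nausea or vomiting within the window, whatever its source, prescriber or prescription status.
2. Explain that definition to subjects for reporting purposes.
3. Make sure such use is recorded with drug, date and time, and source, through 168 h of each cycle. If the study schedule already captures it, only the scoring rule needs to change.

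No rule on when or how patients receive rescue treatment changes.

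The cost is endpoint wording and, if needed, one more data item. CR may read slightly lower, and may be less comparable with the phase III planning rates if that trial used the narrower definition, which the protocol does not state. Precision could also fall a little short: at a comparator CR of 81.5% (assumed share 5%), the width with 57 patients is 0.202 by Wald and 0.216 by Clopper-Pearson, against the 0.2 target.

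The change is best made before the interim analysis at 40% completion. The study period in section 3 starts in June 2025 and this version is dated January 2026, so some cycles may already have been reported under the narrow definition. The amendment should say how those cycles are scored.
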